2.8.1 Biomarkers

Sequencing analyses of cell-free DNA (cfDNA) isolated from the plasma of a subset of subjects who have progressed through treatment with Infigratinib are performed in order to detect genetic alterations from baseline.

2.8.1.1 *Outline of the Data Analysis*

Since the clinical trial was not designed to address specific hypotheses related to subject pre-selection or resistance markers, the analysis of this data should be viewed as exploratory. Analytical results from such analyses may be used to generate additional hypotheses that must then be verified with data derived from subsequent clinical trials. No adjustment for multiple comparisons is planned.

If the number of samples is inadequate to perform a rigorous data analysis, then the available data will only be listed. Additional analyses that may be performed after the completion of the end-of-study clinical study report will be documented in separate reports. These analyses may include but are not limited to the meta-analysis of data from this study combined with data from other studies or the analysis of subject pre-selection or PD markers generated from samples collected during the study but analyzed after the database lock and completion of the clinical study report. Any additional data analysis will be described in an addendum of the SAP or in a stand-alone analysis plan document, as appropriate.

2.8.1.2 *Data Handling Principles*

All measurements below their respective LLOQs or missing data will be labeled as such in the concentration data listings. Measurements below the LLOQ will be treated as zero in summary statistics. Change from baseline analyses will only be performed on subjects with measurable samples and pre- and post-treatment time points.

2.8.1.3 *Data Analysis Principles*

2.8.1.3.1 Analysis Sets

The FAS will be used for all analyses unless otherwise specified. The number of subjects with measurable samples will be identified in the summaries and relevant proportions will be calculated against this number of subjects.

2.8.1.3.2 Basic Tables, Figures, and Listings

Change from baseline for markers measured pre and post baseline to assess the effect on FGFR pathway will be listed by subject and may be summarized by means of descriptive statistics.

Individual CA19-9 serum levels (or change from baseline) will be listed as well as presented as line plots over time. If enough data is available, statistical analysis will be performed in order to assess the relationship between anti-tumor activity (BOR and OS) and CA19-9 levels (or change

from baseline). Best percent change in the sum of longest tumor diameters and the percent change in CA19-9 concentration from baseline will be plotted together in a bar graph.

Subject's FGFR2 gene fusion status in DNA from non-tumor tissue (cell free DNA data) will be listed and compared to the FGFR2 gene fusion status in tumor tissue at baseline; a contingency table will be presented. Genetic alterations detected in cell free tumor DNA will be summarized and presented graphically for subjects with both baseline and post-baseline samples. If there is enough data, change from baseline expression levels will be correlated with efficacy data. Further exploratory analyses will be performed if feasible.

2.9 Interim Analysis

Safety and efficacy data will be continuously monitored by QED Therapeutics in conjunction with the investigators for decision-making purposes.

For Cohort 1, one analysis was performed before Amendment 2 based on the 61 patients enrolled in the study (30 Jun 2016). Protocol amendment 2 restricted enrollment to patients with FGFR2 fusions or translocations, and the formulation was changed from FMI I to FMI III.

After 20 subjects had been treated with FMI III (for at least one cycle) based on Amendment 2, a comprehensive review of all relevant data such as PK, safety, dose interruptions/reductions, and available efficacy was performed. PK, safety, and tolerability data from the first 20 subjects treated with FMI III up to the end of cycle 1 of treatment were assessed and compared with the historical data from subjects treated with FMI I. Upon review of the data, it was decided to continue dosing all subsequent patients treated with FMI III at 125 mg on a 3 weeks on, 1 week off schedule.

In addition, two formal interim analyses for Cohort 1 are planned after Amendment 3:

- The first formal interim analysis for Cohort 1 was conducted when all patients in the Interim Efficacy Analysis Set 1 have been followed for at least 10 months after their initial exposure to the study treatment. This interim analysis will be done using only patients in Cohort 1. Efficacy analysis for this interim analysis will be based on the Interim Efficacy Analysis Set 1 and some key efficacy analyses may be repeated in the FAS. All the other analyses will be conducted on FAS unless otherwise specified.
- The second will be conducted when all the patients who received infiratinib at the time of the first formal interim analysis have at least 10 months follow-up after their initial exposure to infiratinib.

Additionally, for Cohorts 2 and 3, review of data will be performed after a total of 15 patients in either Cohort 2 or 3 have been treated with FMI IV for at least one cycle. A formal interim analysis will be conducted for Cohort 3 when the first dosed 10 patients in Cohort 3 have the potential to complete the second scheduled scan. This interim analysis will only include data from Cohort 3. This is to determine if an additional 10 patients will be added to Cohort 3.

3 SAMPLE SIZE CALCULATION

3.1 Cohort 1

At the time of the first formal interim analysis after amendment 3, the interim efficacy analysis set 1 will include 72 patients with FGFR2 gene fusions or translocations. The half-width of the exact 95% confidence interval for ORR will not exceed 12%.

With at least 106 subjects with FGFR2 gene fusions or translocation will result in the exact 95% confidence interval half-width of ORR less than 10%.

3.2 Cohort 2 and Cohort 3

In Cohorts 2 and 3, patients who are progression-free at the second scheduled post-baseline scan (approximately 16 weeks from treatment initiation) or later will be considered to be benefiting from study treatment. If the lower bound of the patients who are progression-free at the second scheduled post-baseline scan (approximately 16 weeks) or later excludes 20%, the treatment will be considered as benefiting the patients.

For Cohort 2, the percentage of patients who are progression-free at the second scheduled post-baseline scan (approximately 16 weeks) or later will be estimated with 95% exact confidence interval. There will be approximately 20 patients in total. A sample size of 20 will result in the exact 95% confidence interval half width of less than 23%. Patients who withdraw from the study for any reason before the second scheduled scan will be considered as not benefiting from study treatment. Sensitivity analysis will be conducted using the K-M method to estimate PFS >16 weeks.

[Table 8](#) provides some examples of CIs corresponding to observed numbers of patients considered to have benefited from treatment. For example, if 9 of 20 patients are progression-free at the second scheduled post-baseline scan or later, then the lower bound of the 95% exact confidence interval (CI) will exclude 20%.

In Cohort 3, the same definition of benefit rate as for Cohort 2 (the percentage of patients who are progression-free at the second scheduled post-baseline scan [approximately 16 weeks] or later) will be applied. The benefit rate will be estimated with 95% exact confidence interval. The planned enrollment for Cohort 3 is a maximum of 20 patients. With 20 patients, the exact 95% confidence interval half width is <23%. One interim analysis is planned when 10 patients have been dosed and have the potential to be followed up for response for at least 2 scheduled post-baseline scans. If at the interim analysis, ≥ 4 patients are progression-free at the second scheduled post-baseline scan (after approximately 16 weeks) or later, the cohort will continue to enroll the additional 10 patients; otherwise, enrollment will stop at 10 patients. If $\leq 20\%$ patients are benefiting from the study treatment, there is <12.1% chance that the decision after the interim analysis will lead to continuing enrollment.

The percentage of patients considered to have benefited from treatment will be estimated with 95% exact binomial CI. If all 20 patients are enrolled, the exact 95% CI half width will not exceed 23%. [Table 8](#) provides some examples of CIs corresponding to observed numbers of

subjects considered to have benefited from treatment. At the final analysis, if 9 of 20 subjects who are progression-free at the second scheduled post-baseline scan or later, the lower bound of the 95% exact CI will exclude 20%.

Table 8: 95% CI Examples Corresponding to Observed Numbers of Subjects Considered to Have Benefited From Treatment (Cohorts 2 and 3)

| Number of subjects considered to have benefited from treatment | 95% Exact CI |
|--|----------------|
| 4 | (0.057, 0.437) |
| 8 | (0.191, 0.640) |
| 9 | (0.231, 0.685) |
| 10 | (0.272, 0.728) |
| 12 | (0.361, 0.809) |

CI=confidence interval

4 CHANGE TO PROTOCOL SPECIFIED ANALYSES

None.

5 APPENDIX

5.1 Imputation Rules

5.1.1 *AE, CM, and Safety Assessment Date Imputation*

Table 9: Imputation of Start Dates (AE, CM)

| Missing Element | Rule |
|----------------------|---|
| day, month, and year | 
• No imputation will be done |
| day, month | 
• No imputation will be done |
| day | 
• If available month and year = month and year of study treatment start date then
◦ If stop date contains a full date and stop date is earlier than study treatment start date then set start date= 01MONYYYY.◦ Else set start date = study treatment start date.• If available month and year > month and year of study treatment start date then 01MONYYYY• If available month and year < month year of study treatment start date then 01MONYYYY |

Table 10: Imputation of End Dates (AE, CM)

| Subject EOT (Y/N) | Missing Element | Rule (* = min (last treatment date plus 30 days, death date, cut-off date, withdrawal of consent date)) |
|-------------------|----------------------|---|
| N | day, month, and year | 
• Data cutoff date |
| Y | day, month, and year | 
• Completely missing end dates will be imputed by the end date of the on-treatment period* |
| | day, month | 
• If partial end date contains year only, set end date = earliest of 31DecYYYY or end date of the on-treatment period * |
| | day | 
• If partial end date contains month and year, set end date = earliest of last day of the month or end date of the on-treatment period* |

Any AEs and CMs with partial/missing dates will be displayed as such in the data listings.

There should be no cases where AE or CM end dates are partial missing (year is available but month or day or both are missing) if a subject has not ended study treatment (EOT). The above imputations are only used for the calculation of time to and duration of AEs and concomitant medications.

5.1.2 *Death Date Imputation*

If day is missing, then impute to the 1st of the month unless last known to be alive date is greater than the 1st of the month, in that case, set the death date to the last known to be alive date.

5.2 Table of Adverse Events of Special Interest, Search Strategies, and Rationales for Sponsor-Defined Search Strategies

| Adverse Event of Special Interest | Search Strategy |
|--|--|
| Calcium-phosphate homeostasis ¹ 
• Hypercalcaemia• Hyperphosphataemia• Hypophosphataemia | Sponsor-defined grouped PTs |
| Eye disorder ² | Sponsored-defined PTs in SOC Eye disorder: CSR/RPED Eye disorder other than RPED |
| Central serous retinopathy/retinal pigment epithelium detachment (CSR/RPED) ³ | Subset of PTs from SOC Eye disorders |
| Cardiac disorder* | Cardiac failure SMQ [narrow, broad] Myocardial infarction SMQ [narrow, broad] Other ischaemic heart disease SMQ [narrow, broad] Cardiac arrhythmia terms, nonspecific SMQ [narrow] Bradyarrhythmia terms, nonspecific SMQ [narrow] Tachyarrhythmia terms, nonspecific SMQ [narrow] Arrhythmia related investigations, signs and symptoms SMQ [narrow, broad] |
| Acute pancreatitis | Acute pancreatitis SMQ [narrow, broad] |
| Pathological fracture ⁴ | Sponsor-defined PTs |
| Tissue calcification ⁵ | Sponsor-defined PTs |
| Vascular/intravascular mineralization ⁶ | Sponsor-defined Grouped PTs |

* Note: SMQs relating to Torsade de Pointes / QT prolongation and cardiac arrhythmias are part of Minimum Critical Toxicity: Cardiac toxicity Rationales for Sponsor-defined grouped terms:

¹ Sponsor-defined PTs capture the medical concept of hypercalcaemia, hyperphosphataemia, and hypophosphataemia. No SMQs available for these terms.

² Sponsor-defined PTs in the SOC Eye Disorders, including 9 PTs used to characterize CSR/RPED, broadly capture eye related events. No SMQ available for this medical concept.

³ A narrow subset of PTs from SOC Eye Disorder (as selected by an ophthalmologist) are grouped to capture the medical concept of RPED. No SMQ available for this medical concept.

⁴ Sponsor-defined PTs include PTs with 'fracture', which capture the broad medical concept of fractures, recognizing that any fracture could be pathological in nature for the population under study. No SMQ available for this medical concept.

⁵ Sponsor-defined PTs include PTs with 'calcification' and 'calcinosis' which capture the broad medical concept of tissue calcification. No SMQ available for this medical concept.

⁶ Sponsor-defined PTs include PTs with targeted root words (athero, arterio, and sclerosis) and words (arterial, artery, calcification, insufficiency, mineralization, peripheral, and venous) with medical judgement to refine on terms which capture the broad medical concept of vascular calcification/mineralization. No SMQ available for this medical concept.

5.3 AESI: Calcium-Phosphate Homeostasis – Hypercalcaemia, Hyperphosphataemia, and Hypophosphataemia

| AESI | Sponsor-Defined Grouped PTs |
|--------------------|---|
| Hypercalcaemia | Adjusted calcium increased Blood calcium abnormal Blood calcium increased Calcium ionised abnormal Calcium ionised increased Calcium phosphate product increased Hypercalcaemia |
| Hyperphosphataemia | Blood phosphorus abnormal Blood phosphorus increased Hyperphosphataemia |
| Hypophosphataemia | Blood phosphorus decreased Hypophosphataemia |

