#### 6.2.2 Follow-up for toxicities

Patients whose treatment is interrupted or permanently discontinued due to an adverse event or clinically significant laboratory value, must be followed up at least once a week (or more frequently if required by institutional practices, or if clinically indicated) for 4 weeks, and subsequently at 4-week intervals, until resolution or stabilization of the event, whichever comes first. Clinical experts or specialists, such as ophthalmologist. endocrinologist, dermatologist, should be consulted as deemed necessary. Further guidelines and dose modifications for the management of specific study drug induced toxicities (hyperphosphatemia, diarrhea) are provided in Table 5. All patients must be followed up for adverse events and serious adverse events for 30 days following the last doses of BGJ398.

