# Unlike routine safety assessments, SAEs are monitored continuously and have special reporting requirements; see Section 8.2.

All adverse events should be treated appropriately. Such treatment may include changes in study drug treatment including possible interruption or discontinuation, starting or stopping concomitant treatments, changes in the frequency or nature of assessments, hospitalization, or any other medically required intervention. If a concomitant medication or non-drug therapy is given, this action should be recorded on the Adverse Event eCRF.

Once an adverse event is detected, it should be followed until its resolution or until it is judged to be permanent, and assessment should be made at each visit (or more frequently, if necessary) of any changes in severity, the suspected relationship to the study treatment, the interventions required to treat it, and the outcome.

Information about common side effects already known about the investigational drug can be found in the Investigator's Brochure or will be communicated between IB updates in the form of Investigator Notifications. This information will be included in the patient informed consent and should be discussed with the patient during the study as needed.

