- All TEAEs occurred in $\geq 10\%$ subjects by PT by descending order of frequency
- Grade 3 or 4 TEAEs by PT by descending order of frequency
- Treatment related Grade 3 or 4 TEAEs by PT by descending order of frequency
- Treatment emergent serious AEs (SAEs) by PT by descending order of frequency
- Treatment emergent serious treatment-related AEs by PT by descending order of frequency
- TEAE leading to treatment discontinuation by PT by descending order of frequency
- TEAE requiring additional medication or therapies by descending order of frequency

The following listings will be produced:

- All adverse events
- All serious adverse events

Deaths

Primary reason for on-treatment, post-treatment and all deaths will be summarized for the full analysis set. Treatment-emergent AE with fatal outcome will be summarized by SOC and PT. On-treatment death will also be summarized by SOC and PT.

All deaths will be listed and on-treatment death will be flagged.

Adverse Events of Special Interest

Adverse events of special interest (AESI) will be considered. Each AESI consists of one or more well-defined safety events which are similar in nature and for which there is a specific clinical interest in connection with the study treatment(s) (Section 5.2 to Section 5.8). For each specified AESI, number and percentage of patients with at least one event within the AESI will be reported. The following AESI will be considered for this study:

- Calcium phosphate homeostasis, including the subcategories of hypercalcemia, hyperphosphatemia, and hypophosphatemia
- Eye disorder
- Central Serious Retinopathy/Retinal Pigment Epithelium Detachment (CSR/RPED)
- Cardiac disorder
- Acute pancreatitis
- Tissue calcification
- Pathological fracture
- Vascular calcification/mineralization

For each AESI (or its subcategory), the overall summary of the characteristics will be provided. In addition, each AESI will also be summarized by subcategory (as applicable), preferred term and worst grade. The current search strategy for each AESI is documented in Section 5.2.

Minimum Critical Toxicities

Minimal critical toxicities are toxicities that should always be explicitly considered during the planning for the development of every new medicinal product (Section 5.9). Analyses of these are based on FDA guidance as applicable (ie, Drug Induced Liver Injury using Hy's Law per FDA guidance).

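### SAP Table 10 caps incomplete AE and medication end dates at last dose + 30 days, so an imputed end date can precede the recorded month or year and shorten the duration

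*SAP*

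**What the plan says.** SAP Section 5.1.1, Table 10 gives the rules for incomplete end dates of AEs and concomitant medications. For subjects who have ended treatment there are three:

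- Day missing: "set end date = earliest of last day of the month or end date of the on-treatment period".
- Day and month missing: "If partial end date contains year only, set end date = earliest of 31DecYYYY or end date of the on-treatment period".
- Whole date missing: "Completely missing end dates will be imputed by the end date of the on-treatment period".

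An asterisk defines that end (the cap, below) as "min (last treatment date plus 30 days, death date, cut-off date, withdrawal of consent date"). For a subject still on treatment, a completely missing end date goes to the data cut-off, and partial end dates are not expected. The table makes no exception for a recorded month or year later than the cap, and no row refers to the AE outcome. It has no row for complete dates. On use, the section says: "The above imputations are only used for the calculation of time to and duration of AEs and concomitant medications". Listings show incomplete dates as recorded.

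The protocol foresees events that run past last dose + 30 days. Section 8.1.1 says: "Once an adverse event is detected, it should be followed until its resolution or until it is judged to be permanent". Section 6.2.2 requires AEs that interrupt or stop treatment to be followed at least weekly "for 4 weeks, and subsequently at 4-week intervals, until resolution or stabilization of the event". Section 7.1.6 follows drug-related AEs to resolution or stability, but collects AE information in general for 30 days after the last dose. Section 8.1.1 lists outcome as an item separate from the start and end dates.

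The only planned output likely to carry duration is in SAP Section 2.7.2.1.2: "For each AESI (or its subcategory), the overall summary of the characteristics will be provided". Its contents are not itemised.

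**The concern.** An imputation rule for a partial date should respect the part that was recorded. Here, once the recorded month or year falls after last dose + 30 days, the rule moves the end to a date that the site's own entry rules out, and always to an earlier one. The protocol's follow-up provisions generate such entries, mainly for events that outlast treatment.

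The completely missing case raises a related problem. A subject who has stopped drug and whose event carries an outcome of not resolved is still given an end date no later than last dose + 30 days. Table 10 does not separate this from a resolved event whose date was lost.

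At stake are AE and medication durations, including any that appear in the summaries of AEs of special interest (eye disorders, calcium-phosphate homeostasis, tissue calcification and others).

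**Working it through.** The plan states no figure for this point, so there is nothing to reproduce. The check applies Table 10 literally to assumed dates.

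**Inputs from the SAP (Section 5.1.1, Table 10)**
- Cap = min(last dose + 30 days, death, cut-off, consent withdrawal)
- Imputed end, day missing = min(last day of recorded month, cap)
- Imputed end, day and month missing = min(31 December of recorded year, cap)
- Imputed end, all missing and subject off treatment = cap

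**Assumptions**
- Duration = end − onset + 1. The SAP uses this count for exposure (Section 2.5.1.2) but gives no formula for AE duration.
- No death or consent withdrawal. Cut-off is 30 September 2020.
- All dates below are illustrative.

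| Case | Last dose | Cap | Onset | Recorded end | Imputed end | Days by rule | Feasible days |
|---|---|---|---|---|---|---|---|
| A | 1 Mar 2020 | 31 Mar 2020 | 15 Mar 2020 | Jun 2020 | 31 Mar 2020 | 17 | 79–108 |
| B | 10 Jan 2020 | 9 Feb 2020 | 20 Dec 2019 | Mar 2020 | 9 Feb 2020 | 52 | 73–103 |
| C | 15 Nov 2019 | 15 Dec 2019 | 1 Nov 2019 | 2020 | 15 Dec 2019 | 45 | 62–335 |
| D | 10 Jan 2020 | 9 Feb 2020 | 20 Dec 2019 | Jan 2020 | 31 Jan 2020 | 43 | 13–43 |
| E | 10 Jan 2020 | 9 Feb 2020 | 20 Dec 2019 | Feb 2020 | 9 Feb 2020 | 52 | 44–72 |
| F | 10 Jan 2020 | 9 Feb 2020 | 20 Dec 2019 | blank | 9 Feb 2020 | 52 | not known |

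**Case A in full.** The cap is 1 March + 30 days = 31 March. The rule takes min(30 June, 31 March) = 31 March, so duration is 15 to 31 March = 17 days. The recorded month allows 1 to 30 June, that is 79 to 108 days. The shortfall is 79 − 17 = 62 days (62/79 = 78%) to 108 − 17 = 91 days (91/108 = 84%).

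**Cases B and C.** B is short by 73 − 52 = 21 to 103 − 52 = 51 days. C is placed in the wrong calendar year.

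**Cases D and E.** A partial date wholly inside the window goes to the latest feasible day, so it is not understated. In the month that contains the cap, the imputed date is feasible and may be too late or too early.

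**Case F.** The event is given 52 days whatever its outcome. A subject with the same onset who is still on treatment would be given 20 December 2019 to 30 September 2020 = 286 days. The 286 shows how the two rows differ; it is not an observed duration for the subject off treatment.

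**Bounds.** With a blank end date, onset 0, 15 or 30 days after the last dose gives at most 31, 16 or 1 day. Onset at last dose + 40 days gives −9 days, so Table 10 also lacks a guard against an end before onset.

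**The case against.** The strongest defence is that the cap expresses an on-treatment duration. SAP Section 2.1.1.5 limits safety summaries to the on-treatment period, which ends at last dose + 30 days, and Table 10 uses the same endpoint. That is a coherent choice, but the SAP does not state it for durations and does not say that complete end dates are truncated. If they are not, two events that end on the same late day get different durations solely because one day was not recorded.

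The defence is stronger on blank end dates. A reader might infer that every blank end date is an unresolved event and that its censored duration is analysed as completed. The documents do not support this. Outcome is collected separately and includes resolved and unknown categories, so a blank date may be a data gap. SAP Section 1 leaves derived variables to the ADaM Reviewer's Guide and layouts to the output shells, and either could carry an ongoing flag. What stands is that Table 10 itself makes no use of the outcome.

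A reader might also infer that such events were observed as unresolved up to data cut-off. That is not shown. Protocol Section 7.1.6 limits general AE collection to 30 days after the last dose, and Section 6.2.2 allows follow-up to stop at stabilization. For many AEs the cap may lie close to the end of planned observation.

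Finally, no duration table is named. That limits the consequence but does not make the rule correct, because the SAP says these dates feed duration.

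**Conclusion.** The point holds within a limited scope. For subjects off treatment, a partial end date recorded in a month or year later than last dose + 30 days is replaced by a date that contradicts it, and duration is understated. In the worked month-and-year cases the shortfall is 21 to 91 days. A completely missing end date also receives the cap when the collected outcome is not resolved.

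The effect is confined to time-to and duration calculations for AEs and concomitant medications. AE incidence, grade, treatment-emergent status and listings are unaffected. The documents do not say how many events have incomplete end dates, so the effect on any summary cannot be sized.

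A reader might conclude that the drug's toxicities would look more reversible than they are. The documents do not establish that: no reversibility or duration table is specified, partial dates inside the window are set as late as possible, and blank end dates of subjects still on treatment run to cut-off. The rule should be corrected because it is wrong where it applies and cheap to put right.

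**What to change.** In SAP Table 10:

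1. **Partial end dates.** Remove last treatment date + 30 days from the cap and keep death, cut-off and consent withdrawal. Add that no end date is imputed before the first day of the recorded month or year, or before AE onset. With this change, case B becomes 31 March 2020 and 103 days, the top of its feasible range.
2. **Completely missing end dates.** Use the collected outcome. Report events recorded as not resolved as ongoing, censored at last AE follow-up or cut-off, and show their number beside any duration summary. A Kaplan-Meier summary is optional.
3. **If an on-treatment-only duration is intended.** Say so, and truncate complete end dates in the same way. In that case also reconcile the period end: Protocol Section 10.5.2.1 runs the on-treatment period to 90 days after the last dose but starts the post-treatment period at day 31, while the SAP uses 30 days.

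The cost is an edit to Table 10, made through a SAP amendment (or an addendum after database lock, as SAP Section 1 provides), and reprogramming of one derived date. No new data are needed.
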